4.6.3.2. Laboratory and Adverse Event for Hepatic Safety

Hepatic laboratory values include

- alanine aminotransferase (ALT)
- aspartate aminotransferase (AST)
- total bilirubin (TBL)
- direct bilirubin (DBL)
- serum alkaline phosphatase (ALP), and
- gamma-glutamyltransferase (GGT).

When criteria are met for hepatic evaluations, investigators will conduct close monitoring of hepatic symptoms and liver tests, perform a comprehensive evaluation for alternative causes of abnormal liver tests, and complete follow-up hepatic safety CRFs.

Table BDCY.4.1 lists summary tables, figures, and listings (TFLs) for the analysis of hepatic laboratory data.

Table BDCY.4.1. Summary Tables, Figures, and Listings Related to Hepatic Safety

Analysis	Details
Abnormal postbaseline categories – hepatic safety parameters	
ALT: The number and percentage of participants with a measurement greater than or equal to 1 time (1X), 3 times (3X), 5 times (5X), 10 times (10X), and 20 times (20X) the performing laboratory ULN during the postbaseline period will be summarized for all participants with a postbaseline value.
 
AST: The number and percentage of participants with a measurement greater than or equal to 1 time (1X), 3 times (3X), 5 times (5X), 10 times (10X), and 20 times (20X) the performing laboratory ULN during the postbaseline period will be summarized for all participants with a postbaseline value.
 
ALP: The number and percentage of participants with a measurement greater than or equal to 2 times (2X) and 3 times (3X) the performing laboratory ULN during the postbaseline period will be summarized for all participants with a postbaseline value.
 
TBL: The number and percentage of participants with a measurement greater than or equal to 2 times (2X), 5 times (5X), and 8 times (8X) the performing laboratory ULN during the postbaseline period will be summarized for all participants with a postbaseline value.
 
DBL: The number and percentage of participants with a measurement greater than or equal to 2 times (2X) and 5 times (5X) the performing laboratory ULN during the postbaseline period will be summarized for all participants with a postbaseline value.
 
GGT: The number and percentage of participants with a measurement greater than or equal to 2 times (2X) the performing laboratory ULN during the postbaseline period will be summarized for all participants with a postbaseline value.

Treatment-emergent potentially drug-related hepatic disorders	
Potentially drug-related hepatic disorders are defined using a custom query based on the following SMQs:
 
 • Broad and narrow terms in the Liver-related investigations, signs and symptoms SMQ (20000008) • Broad and narrow terms in the Cholestasis and jaundice of hepatic origin SMQ (20000009) • Broad and narrow terms in the Hepatitis non-infections SMQ (20000010) • Broad and narrow terms in the Hepatic failure, fibrosis and cirrhosis and other liver damage SMQ (20000013) • Narrow terms in the Liver-related coagulation and bleeding disturbances SMQ (20000015) 
These SMQs are a subset of the sub-SMQs comprising the full Hepatic Disorders SMQ. Only the sub-SMQs considered applicable to capturing potentially drug-related hepatic disorders are included.
 
The percentage of study participants with at least one of any of the MedDRA preferred terms from any of the above SMQs will be summarized in addition to the percentages for each MedDRA Preferred Term.

Analysis	Details
Hepatocellular drug-induced liver injury screening plot (TBL vs ALT or AST)	Each participant's data is plotted based on their maximum postbaseline TBL (y-axis) and transaminase (ALT or AST, whichever is higher), regardless of the time between the 2 maximum values. Lines represent TBL and transaminase cutoffs of 2X ULN and 3X ULN, respectively. A potential Hy's law case is circled and is defined as having a maximum postbaseline TBL equal to or exceeding 2X ULN within 30 days after maximum postbaseline ALT or AST equal to or exceeding 3X ULN, without cholestasis (defined as ALP less than 2X ULN).
Hepatocellular drug-induced liver injury screening table	The percentages of study participants falling in each of the 3 relevant quadrants of the plot (right upper, left upper, right lower) will be summarized in a table.
Cholestatic drug-induced liver injury screening plot (TBL vs ALP)	Each participant's data is plotted based on their maximum postbaseline TBL (y-axis) and ALP (x-axis), regardless of the time between the 2 maximum values. Lines represent TBL and ALP cutoffs of 2X ULN and 3X ULN, respectively. A potential cholestatic liver injury case is circled and is defined as having a maximum postbaseline TBL equal to or exceeding 2X ULN within 30 days after maximum postbaseline ALP equal to or exceeding 3X ULN.
Cholestatic drug-induced liver injury screening table	The percentages of study participants falling in each of the 3 relevant quadrants of the plot (right upper, left upper, right lower) will be summarized in a table.
List of Participants with potential hepatocellular drug-induced liver injury	Includes participants falling in the right upper quadrant in the Hepatocellular Drug-Induced Liver Injury Screening plot.
List of Participants with potential cholestatic drug-induced liver injury	Includes participants falling in the right upper quadrant in the Cholestatic Drug-Induced Liver Injury Screening plot

Abbreviations: ALP = alkaline phosphatase; ALT = alanine aminotransferase; AST = aspartate aminotransferase;

CRF = case report form; DBL = direct bilirubin; GGT = gamma-glutamyl transferase;

MedDRA = Medical Dictionary for Regulatory Activities; SMQ = Standardized MedDRA Query;

TBL = total bilirubin; ULN = upper limit of normal.

Planned and unplanned measurements will be included. The measurements do not need to be taken at the same blood draw.

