7.1.1. Liver Chemistry Stopping Criteria

The study intervention should be interrupted or discontinued if 1 or more of these conditions occur.

Elevation	Exception
ALT or AST >8x ULN	
ALT or AST >5x ULN for more than 2 weeks	
ALT or AST >3x ULN and either TBL >2x ULN or INR >1.5	In participants with Gilbert's syndrome, doubling of direct bilirubin should be used for intervention interruption or discontinuation decisions rather than TBL >2x ULN.
ALT or AST >3x ULN with the appearance of fatigue, nausea, vomiting, right upper quadrant pain or tenderness, fever, rash, and/or eosinophilia (>5%)	
ALP >3x ULN, when the source of increased ALP is the liver	
ALP >2.5x ULN and TBL > 2x ULN	In participants with Gilbert's syndrome, doubling of direct bilirubin should be used for intervention interruption or discontinuation decisions rather than TBL >2x ULN.

ALP >2.5x ULN with the appearance of fatigue, nausea, vomiting, right upper quadrant pain or tenderness, fever, rash, and/or eosinophilia (>5%)	
---	--

Resumption of the study intervention can be considered only in consultation with the Lilly-designated medical monitor and only if the liver test results return to baseline and if a self-limited, non-intervention etiology is identified.

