8.2.5. Hepatic Monitoring

Close hepatic monitoring

Initiating laboratory and clinical monitoring for abnormal liver laboratory test results

Laboratory tests, including ALT, AST, ALP, TBL, direct bilirubin, GGT, and creatine kinase, should be repeated within 48 to 72 hours to confirm the abnormality and to determine if it is increasing or decreasing, if 1 or more of these conditions occur. This table shows when to repeat laboratory tests.

If a participant with baseline results of...	develops the following elevations:
ALT or AST <1.5x ULN	ALT or AST \geq 3x ULN
ALP <1.5x ULN	ALP \geq 2x ULN
TBL <1.5x ULN	TBL \geq 2x ULN (except for participants with Gilbert's syndrome)
ALT or AST \geq 1.5x ULN	ALT or AST \geq 2x baseline
ALP \geq 1.5x ULN	ALP \geq 2x baseline
TBL \geq 1.5x ULN	TBL \geq 1.5x baseline (except for participants with Gilbert's syndrome)

What to do if the abnormal condition persists or worsens

If the abnormal liver test result persists or worsens, clinical and laboratory monitoring, and evaluation for possible causes of abnormal liver tests should be initiated by the investigator in consultation with the Lilly-designated medical monitor. At a minimum, this evaluation should include physical examination and a thorough medical history, including

1. symptoms
2. recent illnesses, for example, heart failure, systemic infection, hypotension, or seizures
3. recent travel
4. history of concomitant medications, including over-the-counter, herbal and dietary supplements, and
5. history of alcohol drinking and other substance abuse.

Frequency of monitoring

Initially, monitoring of symptoms and liver tests should be done 1 to 3 times weekly, based on the participant's clinical condition and liver test results.

Subsequently, the frequency of monitoring may be lowered to once every 1 to 2 weeks, if the participant's clinical condition and laboratory results stabilize.

Monitoring of ALT, AST, ALP, and TBL should continue until levels normalize or return to approximate baseline levels.

Comprehensive hepatic evaluation

When to perform a comprehensive evaluation

A comprehensive evaluation should be performed to search for possible causes of liver injury if 1 or more of the conditions in this table occur.

If a participant with baseline results of...	develops the following elevations:
ALT or AST <1.5x ULN	ALT or AST \geq 3x ULN with hepatic signs or symptoms ^a , or ALT or AST \geq 5x ULN
ALP <1.5x ULN	ALP \geq 3x ULN

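### The circled potential Hy's law case depends on the dates of two maxima, so a joint elevation goes uncircled when the bilirubin maximum precedes the ALT/AST maximum or follows it by more than 30 days

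*SAP*

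**What the plan says.** SAP Section 4.6.3.2, Table BDCY.4.1, plans a hepatocellular screening plot. Each participant is placed by maximum postbaseline TBL and maximum postbaseline ALT or AST (whichever is higher), with no condition on the time between them. On that plot "A potential Hy's law case is circled", and the case is defined as "maximum postbaseline TBL equal to or exceeding 2X ULN within 30 days after maximum postbaseline ALT or AST equal to or exceeding 3X ULN". A second condition excludes cholestasis by requiring ALP below 2X ULN.

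The cholestatic plot has a rule of the same form: "maximum postbaseline TBL equal to or exceeding 2X ULN within 30 days after maximum postbaseline ALP equal to or exceeding 3X ULN".

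For each plot there is a table of the percentages in three quadrants and a list of everyone in the right-upper quadrant. Neither applies a time or ALP condition. A closing note says that planned and unplanned measurements are both used and that values need not come from one draw.

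Two parts of the protocol bear on this. Section 8.2.5 says that abnormal liver tests "should be repeated within 48 to 72 hours to confirm the abnormality", with monitoring 1 to 3 times weekly at first if the abnormality persists or worsens. Section 7.1.1 lists, among its liver criteria, "ALT or AST >3x ULN and either TBL >2x ULN or INR >1.5", with no reference to maxima or their order.

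**The concern.** The circle is meant to separate elevations that belong together in time, without cholestasis, from two unrelated elevations in the same person. A rule that uses only the dates of the two overall maxima can fail at this, because the draw that holds a participant's highest value need not belong to the joint episode.

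This trial gives the maxima room to separate. One liver episode produces several draws under protocol Section 8.2.5, all of which enter the analysis. The SAP's safety analysis period also includes follow-up, and the last visit is at Week 57, so a later isolated ALT can replace the one from the joint episode.

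At stake is the only definition of a potential Hy's law case in the SAP. Such cases are likely to be few, so one uncircled case could change what the figure shows.

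**Working it through.** The plan states no figure for this rule, so there is none to reproduce. The check applies the rule as written, and an any-pair alternative, to constructed courses.

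**Inputs from the SAP:** TBL ≥2X ULN; ALT or AST ≥3X ULN; window of 30 days after; ALP <2X ULN.

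**Assumed:** all laboratory values below (multiples of ULN). They are illustrations, not trial data. ALP stays below 2X throughout, and same-day values are taken to count.

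**Rule M (literal).** Let d = day of maximum TBL − day of maximum ALT/AST. Circle if both maxima reach their thresholds, 0 ≤ d ≤ 30, and ALP <2X.

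**Rule P (any pair).** Circle if some ALT/AST ≥3X on day s and some TBL ≥2X on day t satisfy 0 ≤ t − s ≤ 30, with ALP <2X.

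| Course | Values | d | M | P |
|---|---|---|---|---|
| 1. TBL peaks first, same episode | Day 183: ALT 4.0, TBL 2.5. Day 186: ALT 6.0, TBL 2.2 | 183 − 186 = −3 | no | yes |
| 2. Later isolated higher ALT | Day 84: ALT 4, TBL 2.5. Day 364: ALT 5, TBL not raised | 84 − 364 = −280 | no | yes |
| 3. ALT rising at first joint elevation, TBL peaks last | Day 100: ALT 4, TBL 2.1. Day 107: ALT 8, TBL 3. Day 114: ALT 6, TBL 4 | 114 − 107 = 7 | yes | yes |
| 4. Both peak at the first draw | Day 100: ALT 5, TBL 2.5. Day 107: ALT 3, TBL 1.5 | 0 | yes | yes |
| 5. Both rise and peak together later | Day 100: ALT 4, TBL 2.1. Day 107: ALT 8, TBL 3 | 0 | yes | yes |
| 6. ALT and AST peak at different draws | Day 100: ALT 5, AST 6, TBL 2.5. Day 107: ALT 8, AST 4, TBL 2.2 | 100 − 107 = −7 (higher of the two); 100 − 100 = 0 (AST) | no, or yes if either maximum may serve | yes |

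Rule M circles 3 of 6, or 4 of 6 if either transaminase maximum may serve. Rule P circles all 6. All 6 lie in the right-upper quadrant, so all are tabulated and listed. The courses were chosen to probe the rule, so 3 of 6 is not a frequency.

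**What causes a miss.** Courses 3 and 5 show that a rising ALT is not enough. The miss needs d < 0 (courses 1, 2 and, on one reading, 6) or d > 30. The second arises when TBL is at least 2X in the joint draw but reaches its overall maximum more than 30 days after the transaminase maximum.

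**Direction of the error.** If rule M circles a participant, the two maxima are themselves a qualifying pair, so rule P circles that participant too. With the ALP condition held the same, rule M can only undercount.

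**Frequency.** This depends on the lag between the two peaks, the draw interval and measurement noise, and the documents give none of these for liver episodes. Simulated single episodes (assumed bell-shaped curves, ALT peak 8X, TBL peak 3.2X, draws every 3 or 7 days, 5–10% noise) left uncircled 10–36% of same-draw cases when the peaks coincide, 0.5–13% when TBL peaks 3 days later, and about 0–1% when it peaks 7 days later. That spread comes from the assumptions and is not an estimate for this trial.

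**The case against.** The strongest reply is that the circle only annotates a figure. No count, test or decision is attached to it. Every course above appears in the right-upper-quadrant table and in the list of potential hepatocellular drug-induced liver injury. Individual evaluation does not use maxima either: under protocol Section 8.2.5, TBL ≥2X ULN alone (baseline below 1.5X ULN, no Gilbert's syndrome) calls for a comprehensive evaluation and the hepatic safety CRF. This stands. A reader might infer that participants drop out of hepatic review, and the documents do not support that.

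A second reply concerns the wording. The sentence could mean the highest TBL within the 30 days after the transaminase peak. If the peak day counts, course 1 is then circled, because Day 186 has ALT 6.0X and TBL 2.2X. That is a fair reading, but it does not rescue course 2, where no TBL ≥2X follows the Day 364 ALT. The text also leaves open whether same-day values count, whether either transaminase maximum may serve, and at which draw ALP is judged. Two programmers could implement it differently.

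Third, a reader might take protocol Section 7.1.1 as contradicting the SAP. It does not. It is a rule for individual participants with strict inequalities, an INR alternative and no ALP exclusion, and a group-level screening display need not match it. It shows only that joint elevation can be recognised without reference to maxima.

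Finally, SAP Section 1 places the figure and listing specifications, and additional safety analyses, in separate documents. A better definition may exist there, but it cannot be seen here.

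**Conclusion.** The point holds in a limited form. Read literally, the SAP's only definition of a potential Hy's law case leaves a same-draw or same-episode joint elevation uncircled when the TBL maximum precedes the ALT/AST maximum or follows it by more than 30 days. The case of a later, unrelated, higher ALT fails on the softer reading as well. The cholestatic rule shares the form.

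A broader claim, that any case with ALT still rising is missed, is wrong: if TBL peaks with ALT or within 30 days after it, the case is circled.

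The consequence is a possible one-sided undercount of circled cases of unknown frequency. It still deserves correction because the quadrant table and list apply neither a time nor an ALP condition, so the circle is the one planned output in this section that marks temporally linked, non-cholestatic elevations. The conclusion rests on the SAP text alone and on the ALP condition being applied in the same way under both rules.

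**What to change.** Keep the maxima for the plot axes, the quadrant table and the list. Redefine the circles in Table BDCY.4.1:

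- **Potential Hy's law case:** any postbaseline TBL ≥2X ULN on the same day as, or within 30 days after, any postbaseline ALT or AST ≥3X ULN, with ALP <2X ULN. State at which draw ALP is assessed.
- **Potential cholestatic case:** any postbaseline TBL ≥2X ULN on the same day as, or within 30 days after, any postbaseline ALP ≥3X ULN.

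Align the figure specifications with this wording. The cost is one sentence per rule and a small programming change, with no new data. The downside is that a few more cases may be circled for review.

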4.6.3.3. Clinical Laboratory Evaluations

For the following selected laboratory measures:

- liver enzyme tests: ALT, ALP, AST, GGT, DBL and total bilirubin
- lipid measures: triglycerides, total cholesterol, low-density lipoprotein (LDL)-C, and high-density lipoprotein (HDL)-C (results from fasting samples)

The MMRM model (as described in Section 4.6) will be used for the observed values, change from baseline and percentage change from baseline, for which log-transformation will be applied. Geometric LS means will be provided. Analyses will be provided in both international units (SI) and conventional units (CN) if they are different.

Box plots with descriptive statistics for the observed values and change from baseline will be provided by treatment group and visit.

For other laboratory measures, descriptive summaries will be provided for the observed values and change from baseline by treatment group and visit.

The percentages of participants with elevated or low values meeting specified levels (see Appendix 10 [Section 6.10]) at any post-baseline (including scheduled and unscheduled measurements) will be summarized and compared between treatment groups using risk difference, odds ratio and 95% confidence interval.

A listing of abnormal laboratory analytes collected quantitatively (high or low during postbaseline using Level 2 definitions in Appendix 10) and qualitatively (abnormal during postbaseline) will be provided, including participant identification, treatment group, laboratory sample collection day (that is, days from the start of study drug), analyte name, abnormal result, and reference low or high limits (Level 2 cut-off value).

Scatter plots of maximum baseline-by-maximum postbaseline measurements and minimum baseline-by-minimum postbaseline measurements will not be created a-priori. They may be created if warranted after review of the planned tables and figures, using Figures 6.3 and 6.4 from the Analysis and Displays for Labs white paper (PHUSE 2022) as the model. Analysis data model (ADaM) datasets will include variables to enable the creation of scatter plots for use in either an interactive tool or for ad-hoc figures.

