9.3.5. Safety Analyses

Safety measures include

- treatment exposure
- AE
- vital signs
- weight
- hypoglycemia
- laboratory measures and
- immunogenicity.

All safety analyses will be based on the SS.

Events that are newly reported after the first dose of LY3209590 or insulin degludec or reported to worsen in severity from baseline will be considered TEAEs. The Medical Dictionary for Regulatory Activities lowest level term will be used in the treatment-emergent assessment. The maximum severity for each lowest level term during the baseline period will be used as baseline severity.

Summary statistics will be provided for incidence of

- TEAEs
- SAEs

- study discontinuation due to AEs
- intervention discontinuation due to AEs, and
- deaths.

For continuous safety variables, such as laboratory measures, vital signs, and weight, the MMRM or ANCOVA models will be used.

For categorical safety variables, such as AEs, incidence of hypoglycemia, treatment-emergent abnormal laboratory measurements, either the Fisher's exact test or logistic regression will be used for treatment comparison.

Hypoglycemia analysis

The participant-reported hypoglycemia will be analyzed using data from the e-diary by

- Level 1 (defined by glucose value ≥ 54 to < 70 mg/dL [3.0 to 3.9 mmol/L])
- Level 2 (defined by glucose < 54 mg/dL [3.0 mmol/L])
- Level 3 (severe hypoglycemia), and
- the composite of Levels 2 and 3.

The analysis periods of 0 to 6, 0 to 12, 0 to 26, 0 to 52, 12 to 26, and 26 to 52 weeks of treatment will be considered. Documented hypoglycemia will be defined as

- All documented hypoglycemia - episodes for the 24-hour period
- Non-nocturnal hypoglycemia - episodes during 6 AM to midnight, and
- Nocturnal hypoglycemia - episodes during midnight to 6 AM.

The incidence and rate of hypoglycemia will be summarized by treatment and analysis period for different types of hypoglycemia.

Further details for assessing all safety measures will be described in the SAP.

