		Edited Section 3, to adjust Efficacy Analysis Set 2 for Efficacy Estimand.	To redefine the cut-off for different analysis and intercurrent events.
		Edited Section 4.1 to update the definitions of baseline and post-baseline observations for different analysis.	For clarity and consistency with data collection.
		Added, in Section 4.2, analysis of time-to-event of interest in disposition.	To align with PSAP.
		Edited Section 4.3.3 for sensitivity analysis of primary endpoint and added Section 4.4.1.3 for sensitivity analysis of key secondary endpoints.	To address regulatory feedback.
		Added subsections to Section 4.4.2.	For clarification of each supportive secondary endpoints.
		Added subsections in Section 4.5.1 to explicitly mention analysis method for tertiary outcome measures. Methodology for multiple imputations for missing data have been updated.	To address regulatory feedback.
		Changes were made throughout Section 4.6.2 1. for laboratory analysis, removed shift analysis, treatment-emergent high/low and add elevated or low values meeting specified levels, and 2. risk difference, odds ratio and 95% will be used for safety categorical data analysis.	To align with PSAP.
		Added Section 4.6.3.1.2 for analysis for CGM-based hypoglycemic events.	Per CGM international consensus statement.

SAP Version	Approval Date	Change	Rationale
		Edited Section 4.7.1 and Section 4.7.2 for clarification and reorganizing of the corresponding analyses. Hence, added Section 6.12 to clarify the interaction effect for subgroup analysis.	For clarity.
		Edited and added texts in Section 6.6 to clarify handling of missing CGM data and definitions of CGM derived hypoglycemic episodes.	Per CGM international consensus statement 2023.
		Remove all contents related to ME2.	No extended enrollment into ME2 cohort is needed for any country in order to meet the regulatory requirement.
		Throughout the SAP made minor changes and reorganization.	For clarity, no change to analysis methodologies, so not detailed.
3	Prior to the database lock	Added treatment regimen analysis for the selected secondary and tertiary endpoints (fasting serum glucose, fasting glucose from SMBG), and selected CGM parameters in Sections 4.1 and 4.4.2.1.	To implement FDA feedback.
		Added missing data at baseline which will be imputed using MI approach under MAR assumption in Section 4.4.1.	Addition.

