4.6. Safety Analyses

Safety measures include treatment exposure, AEs, vital signs, weight, hypoglycemia, laboratory measures, and immunogenicity. All safety analyses will be based on the Safety Analysis Set

(SS). Unless otherwise specified, the safety analysis period will include both the treatment period and follow-up period.

Percentages will be calculated using the SS as the denominator. For events that are sex-specific, the denominator and computation of the percentage will include only participants from the given sex. Unless otherwise noted, Fisher's exact test will be used for the treatment comparison and risk difference and 95% confidence intervals will be provided. Additionally, an odds ratio and 95% confidence intervals will be provided for selected tables in addition to the risk difference.

For continuous safety variables (for example, laboratory measures, vital signs, and weight), descriptive statistics for the observed and change from baseline at scheduled visits during the treatment and the follow-up period will be provided. For selected laboratory measures (that is, liver enzyme tests, lipid measures), observed values, change from baseline, and percentage change from baseline will be analyzed for the log-transformed values by the MMRM model using treatment, visit, and treatment by visit as fixed effects; baseline of the dependent variable as a covariate; and compound symmetry as the variance-covariance structure. The last postbaseline observation in the study will be analyzed by the ANCOVA model with the independent variables of treatment and baseline of the dependent variable.

The incidence and event rate of participant-reported and CGM-based hypoglycemia will be summarized by treatment and analysis period for different types of hypoglycemia. Analysis details are provided in Section 4.6.3.1.

The treatment-emergent analyses will use all data in the analysis period, including scheduled and unscheduled measurements. The safety analysis period for treatment-emergent analyses starts after the first dose and ends at the last visit in the study, including the safety follow-up period.

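### The laboratory tables compare levels met at any post-baseline visit without regard to baseline, in place of the treatment-emergent comparison the protocol names, while SAP 1 and 4.9 report no changes

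*SAP*

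**What the plan says.** Protocol 9.3.5 gives examples of categorical safety variables to be compared by Fisher's exact test or logistic regression. One of them is "treatment-emergent abnormal laboratory measurements".

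The current SAP 4.6.3.3 plans this instead: "The percentages of participants with elevated or low values meeting specified levels (see Appendix 10 [Section 6.10]) at any post-baseline". Scheduled and unscheduled values count, and the arms are compared by risk difference, odds ratio and 95% confidence interval. The rule does not mention baseline status. Yet the table in SAP 4.1 defines a baseline window, from screening to first dose, for laboratory values classed as elevated or low.

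The SAP version history explains the difference. For version 2 it records: "for laboratory analysis, removed shift analysis, treatment-emergent high/low and add elevated or low values meeting specified levels". The reason given is alignment with the PSAP. SAP 1 and SAP 4.9 nevertheless state that the protocol's analyses are unchanged.

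Baseline is used elsewhere. Liver tests and lipids get a repeated-measures model (MMRM) with a baseline covariate. For the rest, "For other laboratory measures, descriptive summaries will be provided for the observed values and change from baseline by treatment group and visit". Plots pairing baseline with post-baseline extremes are optional: "Scatter plots of maximum baseline-by-maximum postbaseline measurements and minimum baseline-by-minimum postbaseline measurements will not be created a-priori". The hepatic categories in SAP 4.6.3.2 are also counted among everyone with a post-baseline value.

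**The concern.** A participant who already meets a cut-off at baseline, and still meets it later, counts as a case in the planned table whichever treatment was given. If such participants are common and equally persistent in both arms, they add the same background to each percentage. The risk difference then shrinks and the odds ratio moves towards 1. A treatment-emergent comparison avoids this, and it is the one the protocol names.

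Several Level 1 cut-offs in Appendix 10 are mild, such as total cholesterol above 200 mg/dL, potassium below 3.6 mEq/L and uric acid above 7.0 mg/dL. Protocol 5.1 and 5.2 set numeric laboratory entry limits only for HbA1c, liver tests and eGFR, so participants can enter the trial already past these levels. What is at stake is the sensitivity of a safety display, and a SAP section on changes that tells its reader there were none.

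**Working it through.** **Step 1. Which rows are affected.** Counted from SAP Appendix 10 (Section 6.10):

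- All rows: chemistry 15 + kidney 2 + lipids 5 + blood count 7 + differential 4 + coagulation 1 = 34.
- Defined relative to baseline: creatinine, eGFR, hemoglobin decrease, hemoglobin increase = 4.
- No scheduled baseline: prothrombin time = 1. It is absent from the scheduled tests in protocol Appendix 2 and appears only in the hepatic work-up (protocol 8.2.5 and Appendix 5).
- Absolute rows with a scheduled baseline: 34 - 4 - 1 = 29.
- Of these, 5 lipid rows also have baseline-adjusted models, and 2 absolute hemoglobin rows have baseline-relative companions. Remaining: 29 - 5 - 2 = 22 (15 chemistry, 3 white-cell or platelet, 4 differential).
- For these 22 rows SAP 4.6.3.3 plans only descriptive summaries of change.

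Hepatic categories in SAP 4.6.3.2: ALT 5 + AST 5 + ALP 2 + total bilirubin 3 + direct bilirubin 2 + GGT 1 = 18. The lowest multiple for each analyte can be present at entry:

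- ALT and AST ≥1x ULN: the entry limit is 3x.
- ALP ≥2x: the entry limit is 2.5x.
- GGT and direct bilirubin ≥2x: no entry limit.
- Total bilirubin ≥2x: exclusion criterion 17 exempts Gilbert's syndrome.

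**Step 2. How much dilution.** The documents give no prevalence, onset or persistence, so every rate here is an assumption. Let b be the baseline prevalence of the level, TE the new-onset proportion among those not meeting it at baseline, and q the proportion of baseline cases who meet it again after baseline.

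- Planned table: p = b·q + (1 - b)·TE, with n = 670/2 = 335 per arm.
- Newly-meeting table: p = TE, with n = 335·(1 - b) per arm.
- Risk difference in the planned table: b·(q1 - q0) + (1 - b)·(TE1 - TE0). With equal persistence this is the new-onset difference times (1 - b).
- Power: two-proportion normal approximation, unpooled variance, two-sided 0.05.

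Example with TE 5% vs 10%, b = 30%, q = 100% in both arms:

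- Planned: 0.30 + 0.70·0.05 = 0.335 against 0.30 + 0.70·0.10 = 0.370. Risk difference 3.5 points, odds ratio 1.17, standard error 0.0369, ratio 0.95, power 16%.
- Newly meeting: 0.05 vs 0.10 with 335·0.70 = 234.5 per arm. Risk difference 5 points, odds ratio 2.11, standard error 0.0242, ratio 2.06, power 54%.

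Power for TE 5% vs 10% (persistence pairs put the higher value in the arm with more new onset):

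| b | Planned, q 100/100 | Planned, q 80/90 | Planned, q 70/90 | Newly meeting |
|---|---|---|---|---|
| 1% | 64% | 66% | 68% | 69% |
| 5% | 47% | 57% | 66% | 67% |
| 10% | 35% | 51% | 66% | 65% |
| 20% | 22% | 46% | 71% | 60% |
| 30% | 16% | 45% | 78% | 54% |

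With a smaller signal (TE 5% vs 8%) at b = 30%, the planned table has 9% (q 100/100) or 30% (q 80/90), against 26% for newly meeting.

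So the newly-meeting view is clearly better when persistence is similar in the two arms. The planned view catches up and then overtakes it as persistence diverges. At rare cut-offs (b = 1%) the choice hardly matters. These tables have no power target, so the figures show relative sensitivity only.

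**The case against.** The other side has several good points.

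- **The change is disclosed.** SAP 4.1 asks that changes and their justification be described in the SAP or the study report, and the version history gives both, if briefly. A reader might infer a concealed change; the documents do not support that. Only the sentences in SAP 1 and 4.9 are wrong.
- **Baseline is not ignored for the 22 rows.** A reader might infer that the SAP has no between-arm comparison using baseline for them. That is too strong. SAP 4.1 gives safety laboratory tests a baseline and scheduled visits for MMRM without limiting this to lipids and liver tests. SAP 4.6 says "The last postbaseline observation in the study will be analyzed by the ANCOVA model", which might be meant for every analyte. Both sit awkwardly with the descriptive-only sentence in 4.6.3.3, so the text is ambiguous. Clinically relevant laboratory changes are also reportable as adverse events (protocol 8.2.4). Treatment-emergent events are new or worse than baseline, and for these Fisher's exact test "will be used for the treatment comparison and risk difference and 95% confidence intervals will be provided". That cover is real but partial, because it depends on investigator judgement.
- **Neither table dominates.** The table in the working shows the order reversing at 70% vs 90% persistence. This argues against replacing the planned table, but not against adding a second view.
- **The PSAP may already hold the comparison.** That cannot be checked here. SAP 1 says this SAP primarily serves the study report and the PSAP covers additional analyses for the Summary of Clinical Safety, so a PSAP analysis might not reach the study report.

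A reader might also infer bias between the arms. Randomization should balance baseline abnormality, so the expected effect is dilution.

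**Conclusion.** The point holds as a modest one. The protocol names a treatment-emergent laboratory comparison, the current SAP replaces it with a comparison that takes no account of baseline status for the absolute cut-offs, and SAP 1 and 4.9 misdescribe this as no change.

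The statistical cost is conditional. It matters for mild cut-offs that are common at baseline and persist similarly in both arms, where the risk difference is multiplied by (1 - b). It is negligible at rare cut-offs and can reverse when persistence differs strongly by arm. Its actual size cannot be found from the documents. These are safety summaries outside the multiplicity-controlled tests, so no primary or key secondary conclusion is affected. Confidence is medium, mainly because the PSAP is not available.

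**What to change.** 1. Keep the planned table in SAP 4.6.3.3.
2. Add a descriptive between-arm comparison (risk difference, odds ratio, 95% confidence interval) of participants newly meeting the Level 1 or worse cut-off. The denominator is participants with a value in the SAP 4.1 baseline window who did not meet the cut-off there. Apply it to the 29 absolute rows with a scheduled baseline. That gives 28 cut-offs, because high bicarbonate has only a Level 3. Levels 2 and 3 are optional.
3. Do the same for the low-multiple hepatic categories: ALT and AST ≥1x, and ALP, GGT, direct bilirubin and total bilirubin ≥2x ULN (6 categories).
4. If the PSAP already supplies this comparison for the study report, a cross-reference is enough.
5. State in SAP 4.9 that the treatment-emergent laboratory comparison was replaced, and why, and correct the sentence in SAP 1. Do not list the shift analysis there, since protocol 9.3.5 does not plan one.

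The cost is one more table, a baseline-status flag and two corrected sentences, with no new data. The datasets are already specified to support similar displays: "Analysis data model (ADaM) datasets will include variables to enable the creation of scatter plots". The downsides are denominators that differ by analyte and 28 + 6 = 34 further unadjusted comparisons. If each were tested at 0.05 with no true effect, about 34 × 0.05 = 1.7 would be expected to reach nominal significance, so the table should be labelled descriptive.
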